# Safety

- Frequency and severity of adverse events and unanticipated adverse device effects (UADEs)
- Evaluation of clinical and laboratory findings
- Concomitant medication assessment
- Frequency and severity of gastrointestinal signs and symptoms (abdominal pain, vomiting, loss of appetite, bloating, flatulence and steatorrhea)

### **Study Duration**

The duration of the study is approximately 7-8 months. Three and a half months will be allocated for patient enrollment. Patient time in study will be at least three and a half months (1 week observation period, 1 week run in, 3 months treatment), and UADEs that occur towards the end of the study may require another 30 days of follow up.

### Study Design

Protocol 0000498 is a multicenter open label study to evaluate the effect of sustained Relizorb use during enteral feeding on fat absorption, as well as safety and tolerability of sustained Relizorb use, in patients with CF and EPI who are receiving enteral tube feeding.

At study entry (Day -14), blood and urine will be collected as part of the screening evaluation and to assess baseline plasma and erythrocyte membrane concentrations of LCPUFAs such as DHA and EPA, plasma concentrations of other long chain fatty acids, plasma concentrations of fat-soluble vitamins, serum protein concentrations, and urinary leukotriene concentrations. Body weight, height, and BMI will be recorded, as well as historical quantification of use of PERT with daytime meals and with enteral feeding. During an initial 7 day observation period subjects will receive their usual enteral nutrition regimen. If subjects use PERT with their enteral nutrition, this will continue through the observation period, and PERT use will be recorded. The subject will also record gastrointestinal symptoms during the observation week in a

Title: Absorption and Safety with Sustained Use of Relizorb™ Evaluation (Assure) Study in Patients With Cystic Fibrosis Receiving Enteral Feeding

gastrointestinal symptom diary. During a 7-day run in period Day -7 to Day -1), subjects will use a standard enteral formula that contains a prehydrolyzed protein (Peptamen® 1.5) at their normal volume of administration from 500 mL up to a maximum volume of 1000 mL per feeding. If subjects use PERT with their enteral nutrition, this will continue through the run in period, and PERT use will be recorded. Throughout the study, individualized patient standard use of PERT with daily meals and snacks will continue.

Following the run in period, subjects will receive an enteral formula similar to Peptamen 1.5 that has a higher long chain triglyceride to medium chain triglyceride ratio (Impact® Peptide 1.5) at their normal volume of administration from 500 mL up to a maximum volume of 1000 mL per feeding using Relizorb in line for the 90 day treatment period.

During the 90-day treatment period, individualized patient standard use of oral PERT is allowed with daily meals, but use of therapeutic agents currently used to aid in fat absorption, such as PERT, will not be used with Relizorb during enteral feedings.

Serial measurements (Days 0, 30, 60, and 90) of plasma concentrations and erythrocyte levels of LCPUFAs such as DHA and EPA, plasma concentrations of other long chain fatty acids, plasma concentrations of fat soluble vitamins, serum protein and concentrations, urinary leukotriene concentrations, and body weight and BMI will be obtained and compared with each other as well as with values obtained at study entry (Day -14).

Safety and tolerability will be assessed using a gastrointestinal symptom diary, as well as recording adverse events (AEs), and unanticipated adverse device effects (UADEs).

Title: Absorption and Safety with Sustained Use of Relizorb™ Evaluation (Assure) Study in Patients With Cystic Fibrosis Receiving Enteral Feeding

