The overall objective of the study is to assess safety and tolerability and demonstrate improved fat absorption with sustained use of Relizorb in patients with CF who have EPI and are receiving enteral nutrition as part of their total nutritional therapy. In this study, subjects will be receiving a semi-elemental formula containing pre-hydrolyzed protein that has a high content of long chain triglycerides (Impact® Peptide 1.5) and will be using Relizorb during their enteral feeding in place of other therapies currently used to aid in fat digestion and absorption, such as pancreatic enzyme replacement therapy (PERT). Plasma concentration of long-chain polyunsaturated fatty acids (LCPUFAs) such as docosahexaenoic acid (DHA; C:22:6n-3) and eicosapentaenoic acid (EPA; C20:5n-3) will be measured as biomarkers of fat absorption. Tissue accretion of LCPUFAs assessed through measurement of erythrocyte membrane concentrations of LCPUFAs such as DHA and EPA, as well as determination of the profile of fatty acids in plasma will also be evaluated as additional biomarkers of fat absorption. Plasma fat-soluble vitamin and serum protein concentrations will also be measured as indicators of effectiveness. All fatty acid, fat-soluble vitamin, and protein concentrations will be assessed in relation to values obtained at the beginning of the run-in period (Day -7), at baseline (Day 0), and during Relizorb use (Days 30, 60, and 90). Safety and tolerability of sustained use of Relizorb will be assessed during use and compared with gastrointestinal symptoms recorded during the observation phase of the study (Day -14 through Day -7).

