#### 7.3 Randomization

Randomization will not be used in this open label study.

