## 11.0 APPENDICES

# 11.1 Peptamen® 1.5 Nutrition Information - *Unflavored* (Nestle Health Science)

One bottle equals 250 mL (1Carton) Amount Per Serving Unit Amount **Amount per Serving** Unit Amount Calories 375 Total Fat \* 14 Kcal g 255 Sodium mg (mEq) Potassium mg (mEq) 465 (12) (11.1)46 Total Carbohydrate G Protein 17 g Vitamin A\*\* IU 1615 Vitamin C 128 mg Calcium 250 Iron 6.75 Mg mg Vitamin D IU 200 Vitamin E IU 11.3 Vitamin K 30 **Thiamin** 0.75 Mcg mg Riboflavin 0.9 Niacin Mg 10.5 mg Folic Acid 200 Vitamin B6 Mg 1.5 mcg Vitamin B12 Mcg 3 **Biotin** 150 mcg Pantothenic Acid Mg 5.25 **Phosphorus** mg 250 lodine 56 100 Mcg Magnesium mg Zinc 9 Selenium 19 Mg mcg 0.75 Manganese 1 Copper Mg mg Chromium 15 Molvbdenum 45 Mca mca Chloride 435 (12.3) L-Carnitine 37.5 mg (mEq) mg **Taurine** 37.5 Choline 170 Mg mg Water 193 mL

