#### Ingredients of Peptamen® 1.5 (Unflavored):

Water, Maltodextrin, Enzymatically Hydrolyzed Whey Protein (from Milk), Medium Chain Triglycerides (from Coconut and/or Palm Kernel Oil), and less than 2% of Cornstarch, Soybean Oil, Soy Lecithin, Magnesium Chloride, Sodium Ascorbate, Sodium Phosphate, Calcium Phosphate, Guar Gum, Calcium Citrate, Choline Chloride, Potassium Chloride, Salt, Sodium Citrate, Taurine, L-Carnitine, Magnesium Oxide, Alpha-Tocopheryl Acetate, Zinc Sulfate, Ferrous Sulfate, Niacinamide, Calcium Pantothenate, Vitamin A Palmitate, Potassium Citrate, Manganese Sulfate, Pyridoxine Hydrochloride, Vitamin D3, Copper Sulfate, Thiamine Mononitrate, Riboflavin, Beta Carotene, Folic Acid, Biotin, Citric Acid, Potassium Iodide, Chromium Chloride, Sodium Selenate, Sodium Molybdate, Phytonadione, Vitamin B12.

\* MCT provides 10 g/250 mL

\*\* Includes 37% of vitamin A activity from beta-carotene

Title: Absorption and Safety with Sustained Use of Relizorb™ Evaluation (Assure) Study in Patients With Cystic Fibrosis Receiving Enteral Feeding

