#### Ingredients of Impact® Peptide 1.5 (Unflavored):

Water, Maltodextrin, Enzymatically Hydrolyzed Whey Protein (from Milk), Medium Chain Triglycerides (from Coconut and/or Palm Kernel Oil), contains less than 2% of L-Arginine Cornstarch, Refined Fish Oil (Anchovy, Sardine), Soybean Oil, Citric Acid, Calcium Citrate, Yeast Extract, Magnesium Chloride, Potassium Phosphate, Ascorbic Acid, Salt, Hdroxylated Soy Lecithin, Sodium Citrate, Choline Chloride, Guar Gum, Xanthan Gum, Potassium Citrate, Taurine, Magnesium Oxide, Sodium Ascorbate, Alpha-Tocopheryl Acetate, L-Carnitine, Zinc Sulfate, Ferrous Sulfate, Niacinamide, Vitamin A Palmitate, Calcium Pantothenate, Manganese Sulfate, Vitamin D3, Copper Sulfate, Pyridoxine Hydrochloride, Beta Carotene, Thiamine Mononitrate, Riboflavin, Folic Acid, Chromium Chloride, Biotin, Sodium Molybdate, Potassium Iodide, Sodium Selenate, Phytonadione and Vitamin B12

Title: Absorption and Safety with Sustained Use of Relizorb™ Evaluation (Assure) Study in Patients With Cystic Fibrosis Receiving Enteral Feeding

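### Relizorb and a fish-oil formula start on the same day in a single arm, so the Day 90 result describes a regimen switch and cannot be credited to Relizorb alone

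*Protocol*

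**What the plan says.** Protocol 7.3 is explicit: "Randomization will not be used in this open label study". There is one arm and no concurrent control.

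The Study Design section of the protocol synopsis describes a 7-day run-in on Peptamen 1.5. On enzymes it says: "If subjects use PERT with their enteral nutrition, this will continue through the run in period". After the run-in, "subjects will receive an enteral formula similar to Peptamen 1.5 that has a higher long chain triglyceride to medium chain triglyceride ratio", namely Impact Peptide 1.5, with Relizorb in line for 90 days and no PERT at feeds. The synopsis Objective says that subjects "will be using Relizorb during their enteral feeding in place of other therapies currently used to aid in fat digestion and absorption".

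The appendices give the ingredients. Impact Peptide 1.5 (11.2) includes "Refined Fish Oil (Anchovy, Sardine), Soybean Oil". The minor ingredients of Peptamen 1.5 (11.1) begin "less than 2% of Cornstarch, Soybean Oil, Soy Lecithin", and its list contains no fish oil.

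SAP 2.2.2 makes the change in erythrocyte DHA+EPA the primary efficacy variable. SAP 8.1 tests it as Day 90 against baseline (Day 0) in a repeated-measures model. The stated aim in Protocol 2.3 and 3.1 and SAP 2.1 is to show that Relizorb improves fat absorption.

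**The concern.** Up to three things change at Day 0: the device is added, the formula is replaced, and PERT at feeds ends for those who used it. The new formula contains a source of the fatty acids that the primary endpoint measures, and the old one lists none. Device and formula change together for everyone, so no analysis of these data can separate their effects.

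The primary test responds to any mean change from Day 0, whatever its cause. A significant result would answer whether DHA+EPA changed after the switch. It would not answer the question in the objectives, which is whether Relizorb improved absorption. Neither document says so, and a report that followed the objectives as written could credit the device with a change that it did not produce alone.

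**Working it through.** **The plan's own figure.** Inputs from Protocol 7.2 and SAP 3.2 and 6.1: n = 30, effect size 0.53, two-sided alpha 0.05. For a one-sample t-test on within-subject change (noncentral t, df = 29, noncentrality 0.53 × √30), power is 0.801. With 0.8/1.5 = 0.533 it is 0.806. The stated 80% reproduces as power for a pre-post change in one group, which is how both documents describe it.

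**What changes at Day 0**

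| Component | Run-in (Day -7 to -1) | From Day 0 |
|---|---|---|
| Relizorb | not part of the run-in | all subjects |
| Formula | Peptamen 1.5 | Impact Peptide 1.5 |
| Fish oil in formula | not listed | listed |
| PERT at feeds | continues where used | prohibited |
| Oral PERT with meals | continues | continues |

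No row separates device from formula. Protocol 4.3 says that the run-in normalises formula type and volume, but it does so on a different formula from the one used in treatment.

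**Size of the formula change (label content per 250 mL, Protocol 11.1 and 11.2)**

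- Peptamen 1.5: total fat 14 g, and "MCT provides 10 g/250 mL". Long-chain fat = 14 − 10 = 4.0 g, which is 4.0/14 = 28.6% of fat.
- Impact Peptide 1.5: total fat 15.9 g at MCT/LCT 50:50. Long-chain fat = 15.9 × 0.5 = 7.95 g, which is 50% of fat.
- Ratio: 7.95/4.0 = 1.99.
- Per 500 mL (×2): 8.0 against 15.9 g. Per 1000 mL (×4): 16.0 against 31.8 g.
- Vitamin A: 3750/1615 = 2.32. Vitamin D: 200 IU in both.
- Vitamin E: 11.3 IU in Peptamen 1.5. The Impact table shows 25 IU in a row whose label is lost.

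The Impact table is broken, so I checked the reading against its energy value, using the 9 and 4 kcal/g in Protocol 2.0. Taking the unlabelled 23.5 g as protein, 15.9 × 9 + 35 × 4 + 23.5 × 4 = 377.1 kcal, against 375 printed. The same sum for Peptamen 1.5 is 14 × 9 + 46 × 4 + 17 × 4 = 378, also against 375. The LCT:MCT ratio moves from 4/10 = 0.4 to 1.0, which agrees with the direction given in the design text.

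**What cannot be computed.** The EPA and DHA content of Impact Peptide 1.5 is not legible here, because several row labels are missing. The documents give no figure for fat hydrolysis in these patients without the device. The formula's contribution to DHA+EPA therefore has no estimate.

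**Direction.** More long-chain fat and added fish oil would favour a rise. Stopping PERT at feeds could work against one. So could earlier Relizorb use, if it raised the Day 0 value: Protocol 4.1.1 admits subjects from Protocol 0000497, and exclusion criterion 14 in Protocol 4.4.2 exempts Relizorb. The sign of the net bias is not fixed.

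**The case against.** The strongest reply has three parts.

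*The bundle is disclosed.* The synopsis Objective and Protocol 3.1 name the formula and the replacement of PERT, and SAP 8.1 claims only mean differences from baseline. This stands as far as it goes. Disclosure is not a limit on inference, though, and SAP 2.1, the objective that the analysis serves, does not mention the formula.

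*The formula alone should do little.* Protocol 2.0 says that long-chain fat must be hydrolysed by lipase before absorption, and that better fat intake or enzymes have not normalised DHA in cystic fibrosis. This is a reasonable expectation, but the trial has no comparison that tests it. Failure to normalise is also not failure to rise, and the primary test needs only a change from Day 0.

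*Nothing in the analysis is miscalculated.* This is right. A reader might infer that the 80% power is wrong or overstated. It is not: it is pre-post power, described as such, and it reproduces.

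Other stronger readings also go too far. A reader might infer that the formula explains any rise, or that the result is biased upward. The documents give neither an EPA/DHA content nor a net direction. Nor does the doubling of long-chain fat imply a doubling of EPA+DHA, since it covers all long-chain fat. And because the Impact table has lost row labels, one cannot say that the protocol omits the EPA/DHA content.

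**Conclusion.** The point holds as a limit on the conclusion. The primary contrast estimates the change in erythrocyte DHA+EPA after moving to Relizorb with Impact Peptide 1.5 and no PERT at feeds. It cannot show that Relizorb itself improved fat absorption, which is what Protocol 2.3 and 3.1 and SAP 2.1 aim to show.

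This rests on the design and the two ingredient lists, not on the arithmetic. The roughly two-fold difference in long-chain fat depends on reading the Impact table as 15.9 g fat split 50:50 by weight. If that reading were wrong, the fish-oil difference and the simultaneous start would remain. The size of the formula effect and the direction of the net bias are unknown. The sample size needs no numerical correction.

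**What to change.** 1. In SAP 2.1 and 8.1, and in Protocol 2.3 and 3.1 if the protocol is amended, state that the primary and other efficacy pre-post tests estimate the change after moving to Relizorb with Impact Peptide 1.5 and no PERT at feeds. The reference is the Day 0 state after the Peptamen 1.5 run-in, with PERT at feeds where used. State that a significant result will not be attributed to Relizorb alone.
2. Apply the limit to every efficacy endpoint whose nutrient supply differs between the formulas. Vitamin A is the clearest legible vitamin example, but it is not the only endpoint concerned.
3. Minor and separate: Protocol 7.8 plans a two-sided Day -14 against Day 0 comparison of laboratory outcomes, and SAP 4.2 promises the analyses identified in the protocol. The SAP 8.1 model uses Visits 2 to 5 only, and SAP Section 10 does not record the comparison as dropped. Either specify it or record that it was dropped. It does not separate formula from device.

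The cost is a narrower claim and a few sentences of SAP text. The model, endpoint and sample size stay as they are. A protocol amendment would need IRB/IEC approval (Protocol 8.2). SAP 3.3 already describes enrolment in the past tense, so the SAP statement is the essential part.

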### STUDY SCHEMATIC

### Table 1: Schedule of Events

	Visit 1	Visit 2	Visit 3	Visit 4	Visit 5 *
Evaluation	Day -14 Study Entry	Day 0 Baseline	Day 30 Treatment	Day 60 Treatment	Day 90 End of Study
Informed Consent	X				
Inclusion / Exclusion Criteria	X				
Demographics	X				
Medical History a	X				
Physical Examination	X				X
Height, Weight, Body Mass Index b	X	X	X	X	Х
Vital Signs c	X	X	X	X	Х
Hematology d	X				X
Clinical Chemistry e	X				Х
Urinalysis f	Х				Х
Blood Lipids g	X	Х	X	Х	X
Serum Proteinsh	Х	Х	X	Х	Х
Serum Pregnancy Test (β-hCG) i	Х				
Urinary Leukotrienes	X	Х	X	Х	X
7-Day Gastrointestinal Symptom Diary	X	X	X	Х	X
Plasma Fatty Acid Samples j	X	X	X	Х	Х
Vitamins A, D, and E k	X	Х	X	Х	X
Peptamen® 1.5 500 to 1000 mL 	Х				
Impact® Peptide 500 to 1000 mL		Х	X	Х	X
Relizorb Administration		×			
Relizorb Accountability Log		X			
Unanticipated Adverse Device Effects		Х			

Note: Tests and procedures should be performed according to the above schedule but changes in scheduled study visits (±4 days) are allowed with permission from the site for holidays, vacations, etc. The amount of blood taken from subjects will be limited to no more than 3 mL/kg in 24 hours and no more than 7 mL/kg over the course of the study.

Title: Absorption and Safety with Sustained Use of Relizorb™ Evaluation (Assure) Study in Patients With Cystic Fibrosis Receiving Enteral Feeding

- \* If any Unanticipated Adverse Device Event (UADE) is reported on Day 90, then a safety follow-up telephone call will occur on Day 91, and the subject will be followed until either resolution of the event or for 30 days, whichever is shorter.
- a. A complete medical history will be obtained.
- b. Height and weight will be measured and recorded, and BMI will be calculated and recorded at each study visit. Four weight and BMI measurements recorded at 3 month intervals over the previous 12 months before Day -14 will be obtained from the medical record.
- c. Vital signs will include blood pressure, pulse rate, respiratory rate and oral/tympanic temperature and will be obtained on in-clinic days.
- d. Hematology includes complete blood count and white blood cell differential.
- e. Clinical chemistry includes albumin, alkaline phosphatase, alanine aminotransferase (ALT), aspartate aminotransferase (AST), bicarbonate, blood urea nitrogen, calcium, chloride, cholesterol, creatine phosphokinase, creatinine, glucose, lactate dehydrogenase, magnesium, phosphorus, potassium, prealbumin, sodium, total and direct bilirubin, total protein, uric acid and A1C levels.
- f. Urinalysis to include bilirubin, blood, glucose, ketones, leukocyte esterase, pH, protein, specific gravity, urinary creatinine and uric acid.
- g. Blood lipids will include total cholesterol, triglycerides (TG), high-density lipoprotein (HDL) and low-density lipoprotein (LDL).
- h. Serum proteins include total protein, prealbumin, albumin, and transferrin.
- i. A serum Beta-Human Chorionic Gonadotropin (β-hCG) pregnancy test will be performed only for females of childbearing potential. Results must be available prior to Day 1.
- j. Blood samples will be obtained for plasma and red blood cell fatty acid analysis.
- k. Blood samples will be collected to measure levels of Vitamins A, D, and E.
- I. Peptamen 1.5 will be administered as the enteral formula during the run in phase from Day -7 through Day -1.

Alcresta Pharmaceuticals, Inc.
Document Status: Approved/Effective

Title: Absorption and Safety with Sustained Use of Relizorb™ Evaluation (Assure) Study in Patients With Cystic Fibrosis Receiving Enteral Feeding

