# 4.2 Study Duration

The anticipated study duration is approximately 104 days. This includes a 7 day observation period when the subject is maintaining their usual care routine, a 7 day run in period, and a 90 day open label treatment period. Subjects who experience a UADE during the last 29 days of the open label period will be followed for 30 days following the occurrence of the UADE or until resolution, whichever comes first.

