# Visits 3, 4, and 5: Treatment Period (Days 30, 60, and 90)

Approximately one week before visits 3, 4, and 5, study staff will contact subjects/parents/caregivers and remind them to start a 7-day gastrointestinal diary such that it is completed the day before the study visit, and also remind them to bring the completed diary with them to the clinic visit along with all used and unused Relizorb cartridges. During these visits study staff will collect the completed 7-day gastrointestinal symptom diary. Blood samples will be collected for fatty acid, protein, and fat-soluble vitamin analysis during these visits. In addition, a urine sample will be collected for urinary leukotriene analysis. Body weight and height will be measured and recorded, and BMI will be calculated and recorded. Study staff will assess UADEs and concomitant procedures and medication use.

Study staff will review the Relizorb Accountability Log for completeness, collect all used Relizorb cartridges, and provide subjects with additional unused Relizorb cartridges for at home use until the next scheduled visit. Concomitant medications and UADEs will be assessed.

Subjects who experienced a new or ongoing UADE within the previous 29 days will receive a follow-up safety contact until 30 days after the occurrence of the UADE or until the UADE has resolved, whichever comes first. Therefore the duration of the study may be extended if a subject has a new or ongoing UADE between Day 60 and Day 90.

On the final clinic visit (Day 90), the majority of baseline procedures will be repeated. End of study procedures will include standard laboratory testing (clinical chemistry, hematology and urinalysis), blood lipids, vital signs, weight, and height measurement, and BMI calculation.

Subjects will be instructed to bring to the clinic all used and unused devices to enable study staff to check administration compliance. All used and unused cartridges will be inventoried and returned to the Sponsor, unless destruction at the study site is authorized.

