## 8.3 Study Monitoring

The monitoring plan and auditing procedures developed or approved by Alcresta will be followed to comply with current good clinical practices (cGCP) guidelines and applicable regulations. The site monitor will visit the site PI and study site at periodic intervals and maintain regular site communication. The site PI and study staff is expected to contact the site monitor directly, regarding clinical questions or clarification of protocol language.

The site PI will prepare and maintain adequate and accurate source documents designed to record all observations and other pertinent data for each subject. The Investigator will allow the Sponsor's representatives, contract designees and authorized regulatory authority inspectors to have direct access to all source documents and medical records pertaining to the subject prior to and during the conduct period of the study. Access to patient records after participation in the study is complete may be required to follow resolution of AEs and UADEs.

Title: Absorption and Safety with Sustained Use of Relizorb™ Evaluation (Assure) Study in Patients With Cystic Fibrosis Receiving Enteral Feeding

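### The follow-up rules for late UADEs disagree on what triggers follow-up and when the 30 days start, and Section 4.3 contradicts itself for events still ongoing at the last visit

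*Protocol*

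**What the plan says.** Four wordings in the protocol, one of them repeated in the SAP, deal with UADEs near the end of treatment.

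- **Protocol Table 1, footnote to Visit 5** (repeated in SAP Section 3.1): "If any Unanticipated Adverse Device Event (UADE) is reported on Day 90, then a safety follow-up telephone call will occur on Day 91". After that, "the subject will be followed until either resolution of the event or for 30 days, whichever is shorter". The trigger is the day of report. The day on which the 30 days start is not given.
- **Protocol Section 4.2:** "Subjects who experience a UADE during the last 29 days of the open label period will be followed for 30 days following the occurrence". Follow-up stops sooner if the event resolves. The trigger is when the event is experienced, and the clock runs from occurrence.
- **Protocol Section 4.3, Visits 3, 4 and 5:** the wording is "new or ongoing UADE within the previous 29 days will receive a follow-up safety contact until 30 days after the occurrence of the UADE". Contact here too stops sooner if the event resolves. The trigger includes events still in progress, and the clock again runs from occurrence. The next sentence describes the interval differently: "the duration of the study may be extended if a subject has a new or ongoing UADE between Day 60 and Day 90".
- **Protocol synopsis, Study Duration:** UADEs late in the study may need a further 30 days. No start day is given.

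Three other places bear on the point. Section 8.3 says that access to records after participation "may be required to follow resolution of AEs and UADEs". Sections 4.5 and 7.4.2 call for best efforts to obtain UADE or safety information from subjects who leave the study.

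**The concern.** The rules for one task differ in three respects: the trigger (reported, experienced, or still in progress), the interval (Day 90 alone, the last 29 days, or Day 60 to Day 90) and the clock start (unstated, or occurrence). Two sites that each follow a passage faithfully could therefore follow the same event for different lengths of time.

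Section 4.3 also has a difficulty of its own. It brings in events still in progress at the visit, but it counts its limit from the day they began. An event that has lasted long enough is covered by the trigger and already past the limit.

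Protocol Section 6.3 treats a UADE as analogous to a serious adverse event. With about 35 subjects at about 10 sites, even one such event followed inconsistently is noticeable in the safety account. What is at stake is consistent follow-up of late serious events. The efficacy analysis is not affected.

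**Working it through.** The plan states no figure to reproduce. The check applies each rule to example events and finds the last possible day of follow-up. Resolution ends follow-up sooner under all the dated rules.

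**Inputs and formulas**

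- Last scheduled visit: Day 90 (Table 1).
- Section 4.2 interval: the last 29 days, taken as Day 90 − 29 + 1 = Day 62 through Day 90. Limit = onset + 30.
- Section 4.3 interval: Day 60 to Day 90 in its second sentence, and it includes events still in progress. Limit = onset + 30.
- Footnote: applies if the event is reported on Day 90. Limit = 90 + 30 = Day 120, assuming that the clock starts on Day 90. If it starts at the Day 91 call, the limit is Day 121.
- Synopsis: gives no start day, so no end day can be calculated.

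**Results**

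| Event | Footnote (Table 1, SAP 3.1) | Section 4.2 | Section 4.3 |
|---|---|---|---|
| Onset Day 90, reported Day 90 | Day 120 | 90 + 30 = Day 120 | Day 120 |
| Onset Day 75, reported Day 75 | not triggered | 75 + 30 = Day 105 | Day 105 |
| Onset Day 75, first reported Day 90 | Day 120 | Day 105 | Day 105 |
| Onset Day 61, reported Day 61 | not triggered | outside Days 62–90 | 61 + 30 = Day 91 |
| Onset Day 55, reported Day 55, ongoing at Day 90 | not triggered | outside Days 62–90 | covered, but 55 + 30 = Day 85 |

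**Reading the rows**

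1. The dated rules agree when onset and report both fall on Day 90.
2. For onset and report on Day 75, Sections 4.2 and 4.3 give 105 − 90 = 15 days after the last visit. The footnote adds nothing.
3. For onset on Day 75 first reported on Day 90, the footnote runs 120 − 105 = 15 days longer than 4.2 and 4.3.
4. Onset on Day 61 shows that the intervals in 4.2 and 4.3 do not quite match, on this day count.
5. For onset on Day 55, the limit passed 90 − 85 = 5 days before the visit at which 4.3 recognises the event as ongoing. This leaves no follow-up after the last visit, although the next sentence says that the study may be extended for such an event.

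In general, with a clock that starts at occurrence, onset + 30 goes beyond Day 90 only if onset is after Day 60.

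**The case against.** The strongest reply is that the footnote is an extra instruction attached to Visit 5 and not a complete rule. It adds a call for events reported that day and does not say that other UADEs stop being followed. Sections 4.2 and 4.3 would then govern everything else, and the 30-day cap is common to all the dated rules. UADEs are assessed at Visits 3, 4 and 5, so the status of the Day 55 event can be recorded on Day 90.

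Much of this stands, and it rules out several stronger readings that a reader might infer:

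- **That the footnote and 4.2 give opposite instructions for 28 of 29 onset days.** The footnote depends on the day of report, not onset, and it is silent about other events. It does not forbid following them.
- **That any event begun by Day 60 and ongoing at Day 90 is past its limit under every rule.** If it is first reported on Day 90, the footnote covers it. An onset on Day 60 reaches its limit on Day 90 and has not passed it.
- **That subjects who withdraw with an ongoing UADE are left uncovered.** Sections 4.5 and 7.4.2 call for best efforts to obtain their information, and 4.3 applies at each treatment visit. No duration is stated, but the matter is addressed.
- **That Section 8.3 expects every event to be followed to resolution.** It only allows for access to records.
- **That the DSMB would lack what it needs.** The triggers in Section 7.2.1 are death, repeated occurrences and an emerging trend. None depends on a final outcome.
- **That outcome is not captured.** The listing shells and eCRF are not available to this review, so this cannot be said.

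The special-case reading does not remove the conflict. When an event from Day 75 is first reported on Day 90, the footnote and Sections 4.2 and 4.3 all apply and end on different days (120 and 105, on the stated assumption). The contradiction within 4.3 does not depend on the footnote at all.

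**Conclusion.** The point holds as a conflict in trigger and clock start, together with an internal contradiction in Section 4.3. In the worked cases the difference is 15 days of follow-up in either direction for an event with onset on Day 75, depending on when it is reported. For an event that began and was reported on Day 55 and is still ongoing at the last visit, no follow-up remains after that visit.

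The figures assume that the footnote's clock starts on Day 90 (one day later if it starts at the call) and that the last 29 days are Days 62 to 90. The Day 55 result needs neither assumption about the footnote, because that event was reported earlier.

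The 30-day cap is not itself an inconsistency, and whether it is long enough is outside this point. The correction should be made because it affects how long sites follow serious late events and costs little.

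**What to change.** 1. Reconcile the synopsis (Study Duration), the Table 1 footnote, Sections 4.2 and 4.3, and the SAP Section 3.1 footnote to one trigger and one clock start. State whether the trigger is report, onset or continuing status.
2. Resolve the contradiction in 4.3 for a UADE still ongoing at the last visit whose limit, counted from occurrence, has already run out.
3. State how the reconciled rule relates to the record-access text in Section 8.3 and to the text on withdrawn subjects in Sections 4.5 and 7.4.2.
4. Confirm that UADE outcome status at last contact is recorded in the eCRF and shown in Listing 16.2.6.3. If it already is, nothing more is needed here.

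The length of follow-up and the rule itself are for the sponsor to decide.

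The cost is wording edits in those five places and possibly a few extra telephone contacts. A listing field is needed only if the check in item 4 finds it missing.
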